1.0 Objectives

1.1 *Describe the purpose, specific aims, or objectives of this research.*

Response: The specific aims of this study are:

[1a] Determine whether low Conscientiousness predicts lesser overall cognitive improvement following cognitive rehabilitation in people with MS.

[1b] Determine whether the impact of Conscientiousness on cognitive rehabilitation is moderated by executive function and treatment adherence.

[2] Identify structural and functional brain connectome characteristics which predict successful improvement in sub-domains of cognition following rehabilitation.

This study will also serve to supplement the sample of participants for the current IRB approved study ((IRB: 603069, Title: *A case-control, 5-year follow-up study of cardiovascular, environmental and genetic risk factors for disease progression in patients with multiple sclerosis (CEG-MS study)*).

1.2 *State the hypotheses to be tested, if applicable.*

NOTE: A hypothesis is a specific, testable prediction about what you expect to happen in your study that corresponds with your above listed objectives.

Response:

[1a] We expect that individuals with low baseline Conscientiousness will experience a lower magnitude of overall cognitive improvement following rehabilitation

[1b] We expect the impact of Conscientiousness on fidelity of rehabilitation will in part be moderated by individual differences in program adherence and executive function

[2a] We expect that individual differences in structural and functional connectome disturbances will in part explain differences in participant responses to cognitive rehabilitation.

2.0 Scientific Endpoints

2.1 Describe the scientific endpoint(s), the main result or occurrence under study.

*NOTE: Scientific endpoints are outcomes defined before the study begins to determine whether the objectives of the study have been met and to draw conclusions from the data. Include primary and secondary endpoints. Some example endpoints are: reduction of symptoms, improvement in quality of life, or survival. Your response should **not** be a date.*

Response: Our primary end-point are predictive. Our first primary end-point will have been met if baseline measures of personality, as measured by the NEO-Five Factor Inventory (NEO-FFI), will predict overall cognitive improvement following rehabilitation. Likewise, our second primary end-point will have been met if baseline measures of brain connectivity predict specific improvements in cognitive sub-domains, following rehabilitation. Cognitive improvement will be measured according to changes from visit 1 to visit 2 for the following neuropsychological tests: Symbol Digit Modalities Test (SDMT), California Verbal Learning Test 2nd Edition (CVLT), Brief Visuospatial Learning Test Revised (BVMT-R), MS Neuropsychological Screening Questionnaire (MSNQ), Delis-Kaplan Executive Function System (DKEFS) Sorting Test, Tower of London (TOL), Elithorn's Perceptual Maze Test (EPMT).

	Day 0 (Visit 1)	Day 90 (Visit 2)
NEO Five Factor Inventory (NEO-FFI)	X	X
Symbol Digit Modalities Test (SDMT)	X	X
California Verbal Learning Test Second Edition (CVLT)	X	X
Brief Visuospatial Memory Test Revised (BVMT)	X	X
MS Neuropsychological Screening Questionnaire (MSNQ)	X	X
Delis Kaplan Executive Function System Tower Test (DKEFS-TT)	X	X
Delis Kaplan Executive Function System Sorting Test (DKEFS-ST)	X	X
Elithorn's Perceptual Maze Test (EPMT)	X	X
Multiple Sclerosis Quality of Life (MSQoL)	X	X
Beck Depression Inventory Fast Screen (BDI-FS)	X	X
Fatigue Severity Scale (FSS)	X	X

3.0 Background

3.1 Provide the scientific or scholarly background, rationale, and significance of the research based on the existing literature and how it will contribute to existing knowledge. Describe any gaps in current knowledge. Include relevant preliminary findings or prior research by the investigator.

Response: The personality trait Conscientiousness is a behavioral phenotype encompassing the proclivity for achievement striving, organization, and deliberation in daily activity. Trait Conscientiousness is operationally measured using the NEO Five Factor inventory (NEO-FFI), a model of personality widely studied in MS and other neurological populations.¹ Trait Conscientiousness is normally distributed in humans, shows substantial cross-observer agreement, and has a similar mean and range across different cultures.^{2,3}

Decreased Conscientiousness relative to healthy controls (HCs) has been observed in people with multiple sclerosis (pwMS)⁴, an autoimmune disease that involves both neuroinflammation and neurodegeneration.⁵ It is important to study Conscientiousness decline in pwMS because preliminary findings suggest that **Conscientiousness predicts poor adaptation and unfavorable disease outcomes in neurological disease**. For instance, Conscientiousness predicts CD4 count and viral load over 1-year in HIV disease.⁶ Lower Conscientiousness is associated with increased risk of amnestic mild cognitive impairment, and transition to Alzheimer's dementia over 12 years.⁷ This trait also correlates negatively with mortality risk among older adults following stroke.⁸ Low baseline Conscientiousness is also associated with increased risk of poor disease outcomes in non-neurological diseases. For instance, adults with prediabetes and low Conscientiousness are more likely to later develop type II diabetes, and children with type I diabetes and low Conscientiousness exhibit worse glycemic control.^{9,10} Notably, **low Conscientiousness is also associated with reduced success of behavioral interventions on health behaviors and disease outcomes**. For example, low Conscientiousness is prospectively associated with reduced improvement in medication adherence, emotional burden, and physical activity, following a range of behavioral interventions in adults with diabetes.¹¹

Lower trait Conscientiousness may also predict less favorable disease course and response to intervention in pwMS. In cross-sectional studies, lower Conscientiousness correlates with impaired processing speed, the hallmark of MS associated cognitive impairment.¹² Low conscientiousness also predicts transition from employment to disability, after controlling for the influence of other factors such as cognitive impairment and depression.^{13,14}

The association between low Conscientiousness and poor functional outcomes in pwMS may be due to differences in behavior, such as reduced adherence to disease modifying therapies.¹⁵ Results from a study in people with Alzheimer's disease implicates a role of executive function, moderating the effect of Conscientiousness on disease outcomes.¹⁶ The impact of low Conscientiousness on successful behavioral intervention in pwMS remains unstudied. One investigation of pwMS showed a correlation between reduced success of cognitive training and poor adherence.¹⁷ Thus, we hypothesize that poor adherence and differences in moment-to-moment intention during similar training interventions would be a function of low baseline Conscientiousness. One study validates

this hypothesis, showing that HCs with low Conscientiousness experience reduced near and far transfer effects following a working memory training.¹⁸

In addition to the application of personality measures, studies have also shown that baseline patterns of brain connectivity can be applied to predict cognitive improvement following training in neurologic disease populations.¹⁹ There is growing interest in the study and application of structural and functional brain network measures in neurologic disease²⁰ and its relationship with cognitive remediation.²¹

Our goals for this research are two-fold. First, we aim to demonstrate the value of personality assessment as a means of risk-stratification and for directing behavioral interventions in pwMS. In order to address our first goal, we will investigate the value of personality assessment as a means of predicting successful behavioral interventions. In our analysis, we will study whether or not the impact of baseline Conscientiousness on successful cognitive intervention is moderated by other behavioral variables, such as program adherence and executive function, higher order reasoning.

In order to address our second goal, we will use a multi-parametric approach in which we account for cerebral pathology, such as regional gray matter atrophy, microstructural white matter damage, lesion volume and localization, white matter tract integrity and structural connectivity, and resting state functional connectivity. We will apply network-based analysis, where appropriate, in order to account for network-level organization of the brain. These methods of analysis are well-suited for elucidating patterns of insult which lead to changes in complex emergent phenomenon such as higher level cognition.

Our results may provide foundation for better directing rehabilitation and behavioral treatments. For instance, a short questionnaire could be used to identify patients whose personality profile puts them at greater risk for unfavorable disease progression. An understanding of this risk could help direct efforts which mitigate against these unfavorable outcomes. Similarly, baseline patterns of cerebral pathology could also be employed to predict responses to the cognitive and other behavioral interventions. There is a burgeoning interest in personality trait adaptation and personalized health plans among health care agencies²² and we believe our research will contribute meaningfully to this growing field of interest.

3.2 Include complete citations or references.

Response:

2. McCrae RR. Trait psychology and culture: exploring intercultural comparisons. *J Pers*. 2001;69(6):819-846.
doi:10.1037/0022-3514.52.1.81.

4.0 Study Design

4.1 *Describe and explain the study design (e.g. case-control, cross-sectional, ethnographic, experimental, interventional, longitudinal, observational).*

Response: Interventional

5.0 Local Number of Subjects

5.1 *Indicate the total number of subjects that will be enrolled or records that will be reviewed locally.*

Response: We will recruit 50 subjects with multiple sclerosis who are already enrolled in CEG-MS study.

5.2 *If applicable, indicate how many subjects you expect to screen to reach your target sample (i.e. your screen failure rate).*

Response:

We expect that potential participants to be enrolled through the CEG-MS study for suitability for the study. Subjects who agree to participate and pass screening requirements will be enrolled in the study.

5.3 Justify the feasibility of recruiting the proposed number of eligible subjects within the anticipated recruitment period. For example, how many potential subjects do you have access to? What percentage of those potential subjects do you need to recruit?

Response: This research will be conducted through the Buffalo Neuroimaging Analysis Center (BNAC) group. We expect to recruit subjects from the CEG-MS study database. Based on our targeted population, we believe there is a sufficient number of potential participants to meet participant target of 50 in adherence to the protocol.

6.0 Inclusion and Exclusion Criteria

*6.1 Describe the criteria that define who will be **included** in your final study sample.*

NOTE: This may be done in bullet point fashion.

Response:

For all subjects:

- males and females above age 18
- fluent in English
- education >9 years

Additional inclusion criteria for MS patients are as follows:

- Clinically definite MS diagnosis
- Expanded Disability Status Scale (EDSS) ≤ 6.5
- MS patients must be relapse-free and stable from the time of their MRI acquired for the CEG-MS study
- Willing and able to comply with the study procedures for the duration of the trial

*6.2 Describe the criteria that define who will be **excluded** from your final study sample.*

NOTE: This may be done in bullet point fashion.

Response:

- history of serious medical or psychiatric illness (other than MS in the patient group) that may affect cognitive functioning
- color-blindness

- history of developmental disability
- past or current alcohol or substance dependence
- History of major depressive disorder, bipolar disorder, or psychotic disorder predating the onset of MS
- History of traumatic brain injury as defined by trauma causing loss of consciousness or transient post-traumatic or retrograde amnesia exceeding 5 min
- Other pathology related to MRI abnormalities

6.3 *Indicate specifically whether you will include any of the following special populations in your study using the checkboxes below.*

NOTE: Members of special populations may not be targeted for enrollment in your study unless you indicate this in your inclusion criteria.

Response:

- Adults unable to consent
- Individuals who are not yet adults (infants, children, teenagers)
- Pregnant women
- Prisoners

6.4 *Indicate whether you will include non-English speaking individuals in your study. Provide justification if you will exclude non-English speaking individuals.*

*In order to meet one of the primary ethical principles of equitable selection of subjects, non-English speaking individuals may **not** be routinely excluded from research as a matter of convenience.*

In cases where the research is of therapeutic intent or is designed to investigate areas that would necessarily require certain populations who may not speak English, the researcher is required to make efforts to recruit and include non-English speaking individuals. However, there are studies in which it would be reasonable to limit subjects to those who speak English. Some examples include pilot studies, small unfunded studies with validated instruments not available in other languages, studies with numerous questionnaires, and some non-therapeutic studies which offer no direct benefit.

Response: Non-English speaking individuals will not be able to have a neuropsychological assessment battery administered as measures are developed in English and no translations are available. Thus non-English speaking individuals will not be involved in the research.

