9.0 Recruitment Methods

N/A: This is a records review only, and subjects will not be recruited. NOTE: If you select this option, please make sure that all records review procedures and inclusion/exclusion screening are adequately described in other sections.

9.1 Describe when, where, and how potential subjects will be recruited.

NOTE: Recruitment refers to how you are identifying potential participants and introducing them to the study. Include specific methods you will use (e.g. searching charts for specific ICD code numbers, Research Participant Groups, posted advertisements, etc.).

Response:

Potential participants will be identified from the pre-existing list of study participants of the CEG-MS study database. Recruitment will be directed towards subjects who completed MRI evaluation for the CEG-MS study. These individuals will then be further screened based on the inclusion and exclusion criteria and contacted in person and via phone. If they are interested, the remaining screening questions will be asked. If the individual agrees to participate in the study, their appointment for testing will be scheduled based on their availability and convenience.

9.2 *Describe how you will protect the privacy interests of prospective subjects during the recruitment process.*

NOTE: Privacy refers to an individual's right to control access to him or herself.

Response:

Contact information from CEG-MS study databases is retained on a secure network in Buffalo Neuroimaging Analysis Centre (BNAC). The network is password protected and can only be accessed by PI and trained study members. Information is de-identified within the contact information file and only those with access to both that file and a separate de-identifying key file called 'CEG Codes' will be able to link the potential participant's name to his/her contact information. Once a participant has been recruited, his/her information will be removed from the recruitment contact information file.

9.3 *Identify any materials that will be used to recruit subjects.*

NOTE: Examples include scripts for telephone calls, in person announcements / presentations, email invitations.

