If an individual is ineligible for participation, their screening information will be discarded (i.e., shredded). If participants are deemed eligible (either in person or over the phone), they will be scheduled to come in to the hospital for neuropsychological testing. Written consent will be obtained prior to administration of tests. As part of the consent process, participants will be asked for permission to use any data collected as part of the screening process as well.

10.2 Describe what data will be collected.

NOTE: For studies with multiple data collection points or long-term follow up, consider the addition of a schedule or table in your response.

Response: Demographic/social history, health history (as provided by participants during screening, review of medical records, etc.), and cognitive test data.

10.3 List any instruments or measurement tools used to collect data (e.g. questionnaire, interview guide, validated instrument, data collection form).

Include copies of these documents with your submission.

Response: Below is a list of neuropsychological tests that will be included. Symbol Digit Modalities Test (SDMT), California Verbal Learning Test 2nd Edition (CVLT), Brief Visuospatial Learning Test Revised (BVMT-R), Delis-Kaplan Executive Function System [DKEFS] Sorting Test, Delis-Kaplan

Executive Function System [DKEFS] Tower Test. Self-report/informant-report surveys have been uploaded. Self-report measures include the Beck Depression Inventory-Fast Screen (BDI-FS), Multiple Sclerosis Neuropsychological Questionnaire (MSNQ), Fatigue Severity Scale (FSS), NEO-FFI personality inventory, Multiple Sclerosis Quality of Life (MSQoL) and Elithorn's Perceptual Maze Test (EPMT). Informant-report measures include the NEO-FFI.

10.4 Describe any source records that will be used to collect data about subjects (e.g. school records, electronic medical records).

Response: We will be collecting MRI and EDSS information for subjects from the database of IRB no. 603069 of CEG- MS study.

*10.5 Indicate whether or not **individual** subject results, such as results of investigational diagnostic tests, genetic tests, or incidental findings will be shared with subjects or others (e.g., the subject's primary care physician) and if so, describe how these will be shared.*

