11.0 Study Timelines

11.1 Describe the anticipated duration needed to enroll all study subjects.

Response: It is anticipated that enrollment of all study subjects will be completed in one to one-and-a-half years.

11.2 Describe the duration of an individual subject's participation in the study. Include length of study visits, and overall study follow-up time.

Response:

Patients will complete two visits (Day 1 and Day 90). Neuropsychological testing will take approximately 1-2 hours during a single visit.

11.3 Describe the estimated duration for the investigators to complete this study (i.e. all data is collected and all analyses have been completed).

Response:

Completion of this study, including primary analyses is expected to be in one to two years.

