NOTE: This may not apply to certain types of studies, including chart/records reviews, survey studies, or observational studies. This question is asked to elicit whether the investigator has an adequate sample size to achieve the study objectives and justify a conclusion.

Response: Given a 0.38 effect size observed in a previous study of HCs which indicated a relationship between Conscientiousness and successful cognitive training²⁰, power analysis indicated 41 participants would be sufficient for an 80% chance of avoiding type II error.

17.3 Describe any procedures that will be used for quality control of collected data.

Response:

All MRI data has already been reviewed for quality by expert investigators responsible for the CEG-MS study.

Scoring and data entry will be completed and checked by trained staff members under the supervision of the PI.

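### Aim 2 uses an existing parent-study MRI as the baseline connectome, with no limit on its age at visit 1, no definition of stable, and no use of the scan-to-visit interval in the analysis

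*Protocol*

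**What the plan says.** Protocol 2.1 states that "our second primary end-point will have been met if baseline measures of brain connectivity predict specific improvements in cognitive sub-domains" following rehabilitation. The schedule in that section lists no MRI at either visit, and Protocol 10.1 describes both visits as performance testing and questionnaires.

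The images come from the parent study. Protocol 10.4: "We will be collecting MRI and EDSS information for subjects from the database of IRB no. 603069 of CEG- MS study". Protocol 9.1: "Recruitment will be directed towards subjects who completed MRI evaluation for the CEG-MS study". Protocol 17.3: "All MRI data has already been reviewed for quality by expert investigators responsible for the CEG-MS study". Protocol 1.1 gives the parent study's title as "A case-control, 5-year follow-up study of cardiovascular, environmental and genetic risk factors for disease progression in patients with multiple sclerosis".

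One criterion connects the scan with visit 1, in Protocol 6.1: "MS patients must be relapse-free and stable from the time of their MRI acquired for the CEG-MS study". It has no time limit, and the Protocol does not say how stability is judged. On timing, Protocol 11.1 expects that "enrollment of all study subjects will be completed in one to one-and-a-half years".

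For aim 2, Protocol 17.1 and the SAP choose models by the distribution and dimensionality of the connectome variables and assess fit by k-fold cross-validation. Neither mentions the time between scan and visit 1.

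**The concern.** A baseline predictor is normally understood to describe the subject at, or close to, the start of the intervention. As written, the plan lets a CEG-MS scan of any age fill that role, provided the patient has been relapse-free and stable since. The predictors that the Protocol's background section names for the second goal include regional atrophy, microstructural white matter damage, lesion volume and resting-state connectivity. Any of these can change in a patient who has had no relapse.

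What is at stake is what aim 2 can conclude. If scans differ in age and the interval is not recorded, a null result cannot separate a connectome that does not predict from a scan that no longer describes the patient. For a positive result, the reader cannot tell over what lead time the prediction holds. A lesser worry is that an older scan requires a longer stable period to qualify, so scan age may be related to disease course.

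**Working it through.** **The plan's own figures.** There is none to reproduce on this point. The documents give no scan date, no interval and no power calculation for aim 2. The only sample size, 41 in Protocol 17.2, is for Conscientiousness (effect size 0.38, 80% power) and is not an input here. Read as a correlation at a one-sided 0.05 level (an assumption), it comes close: ((1.645 + 0.842) / atanh 0.38)² + 3 = 41.6.

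**Step 1: does anything bound the interval?**
- Visits: no MRI (2.1, 10.1).
- Recruitment: anyone with a completed CEG-MS MRI, with no window and no ordering by scan date (9.1).
- Eligibility: relapse-free and stable since the scan, with no maximum (6.1).
- Verification: EDSS also comes from the CEG-MS database (10.4), and the visit schedule lists no new EDSS, so no stated measurement confirms stability at visit 1. Screening uses a script and form (8.1), which are not in the documents.
- Analysis: the interval is not used (17.1, SAP).

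Nothing bounds it.

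**Step 2: can intervals be unequal?** If the scans all predate enrolment, as 17.3 suggests, visit dates spread over 12 to 18 months could by themselves spread scan ages by up to 12 to 18 months, even had every scan been taken on one day. Any spread in CEG-MS scan dates would add to this, but those dates are not given. If instead subjects are approached soon after a CEG-MS scan, intervals would be short and similar.

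**Step 3: what would an outdated scan cost?** Let ρ be the correlation between a connectome measure at the scan and the same measure at visit 1. If the scan relates to training gain only through the visit 1 state, then

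observed r = ρ × true r, and observed R² = ρ² × true R².

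The documents give no value for ρ. For illustration only, take a true r of 0.38 (borrowed from aim 1a), n = 50 and two-sided α = 0.05, with power = Φ(atanh(observed r) × √47 − 1.96):

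| Assumed ρ | Observed r | Share of R² kept | Power |
|---|---|---|---|
| 1.0 | 0.380 | 1.00 | 78% |
| 0.95 | 0.361 | 0.90 | 74% |
| 0.9 | 0.342 | 0.81 | 69% |
| 0.8 | 0.304 | 0.64 | 58% |

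The power column is for a single correlation. It is not the power of a cross-validated multivariate model, and it shows direction and rough scale only. The loss arises only if patients change rank between scan and visit 1; a drift shared by all leaves ρ at 1.

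**The case against.** The strongest reply is that nothing shows the scans to be old. The five years are in the parent study's title, which says nothing about when the MRI was done. Protocol 1.1 calls CEG-MS a current study, 5.2 expects participants to come through it, and 9.1 allows contact in person, all of which fits approach soon after the scan. The enrolment period is not a scan age. The Protocol also saw the gap and dealt with it clinically: the criterion excludes any relapse since the scan and requires stability too. An earlier scan is a legitimate pre-treatment predictor, cross-validation would reflect any lost accuracy, and attenuation makes success harder to claim rather than easier.

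Most of this stands. A reader might infer that the predictors are several years out of date, or that scan age confounds the link between connectome and gain. The documents support neither. The first needs scan dates that are not given. The second needs scan age to be related both to the connectome and to 90-day training gain, and nothing is offered for the latter link.

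The reply does not close the gap. The criterion limits which patients qualify, not how long ago they were scanned, and its second half is undefined. Cross-validation would show poor accuracy but, with no interval recorded, could not show whether scan age was the reason.

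**Conclusion.** The point holds as a gap in specification, with a cheap remedy. What is certain from the text: the second primary end-point rests on a scan this study does not acquire, no rule limits its age at visit 1, stable is undefined, and the interval does not enter the aim 2 analysis. Unequal scan age is possible, but its extent is unknown.

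The size cannot be derived from the documents. With an assumed scan-to-visit 1 correlation of 0.9, 0.9 of the true correlation and 0.81 of R² would remain; with short intervals the loss could be negligible. Confounding remains a possibility only. It would go too far to say that the end-point is invalid or that aim 2 is underpowered because of this.

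**What to change.** - **Protocol 9.1:** approach eligible candidates in order of scan recency.
- **Protocol 6.1:** state how stability since the MRI is judged, and from what source. Look up the scan dates in the CEG-MS database; only if they show that 50 subjects can still be reached, add a maximum MRI-to-visit 1 interval, fixed before enrolment.
- **Protocol 17.1 and SAP, aim 2:** derive the interval for every subject and report its distribution. Include it in the aim 2 models, handled inside the cross-validation folds. Because a main effect for interval does not undo attenuation, also check descriptively whether out-of-fold prediction error rises with the interval. This is preferable to refitting in the half with the most recent scans, since about 25 of 50 subjects are too few for a connectome model.
- **Protocol 2.1:** if intervals prove long, describe the predictor as prior rather than baseline MRI.

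Cost: an ordering of recruitment calls, one derived variable, one extra model term at n = 50 and one descriptive check. No new MRI is needed. A cap would shrink a single-source pool by an amount that cannot be known without the scan dates, so it should stay conditional.
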